Project Protocol

Date final revised: 2018-02-09

Project title:

“Postoperative treatment with Efficacy Safety Score and wireless patient monitoring system at a general ward: a randomised controlled study.”

Authors:

[name] (MD, phd candidate)

[name] (MD, prof. dr.med, main supervisor)

Institution:

Clinic of Anaesthesia and Intensive care, St. Olavs Hospital, Orkdal Department, Trondheim University Hospital, Norway.

Part of larger project

«Development and use of novel tools for assessing efficacy, side-effects and safety of postoperative treatment»

Introduction

In modern perioperative care safety is a primary concern, and in-hospital mortality was recently reported to be 0.5% [1]. Much more frequent, although less serious, are the problems of patient perceived quality in the post-operative period. In a survey of 2252 patients, 55% reported that they suffered from unsatisfactory pain treatment postoperatively [2]. A recent review of 183 studies with more than 100.000 patients, showed a high incidence of adverse effects of postoperative pain treatment. Twenty-five per cent of the patients suffered from nausea, 20 % from vomiting, 14.7 % from pruritus and 23 % from urinary retention. Notably, 24 % of the patients received insufficient doses of analgesics for their pain [3]. Side effects were most typically induced by opioid analgesics. It might be argued that health care personnel should aim at better surveillance of both effects and side effects of analgesics. Lack of feedback on the effects of administration of analgesics, especially of opioids, together with insufficient monitoring of respiratory and circulatory variables, may lead to under-dosing out of fear of side effects. Administration of analgesics may also cause inadvertent over-dosing and even fatal outcomes in hospital as well as at home after discharge [4-8]. As long as the patients remain in the post-anesthesia care unit (PACU) with continuous monitoring and observation, there are abundant tools and measures at hand to ensure both quality and safety of the treatment. On the contrary, after discharge to an ordinary ward, there are less staffing and monitoring resources, and patients may even be left alone for shorter periods.

We hypothesized that medical personnel may benefit from the feedback of a simple monitoring system, which detects changes in respiration - and circulation variables in combination with the patient's subjective experiences of postoperative quality of care. Such a system would be useful, both for the treatment of individual patients as well as for assessing the efficacy and safety of postoperative care given to different groups of patients. We started with an algorithm-based monitoring system with multiple simultaneously recorded variables, as a prototype tool for assessment of quality and safety of postoperative treatment [9, 10]. After a successful pilot study on this narratively developed tool, called Efficacy – Safety Score (ESS), Table 1, we decided to develop this through a documentation and validation process. The results from this are published as the 1st article in this project [11]. As described in this paper there is no such clinical tool as ESS presented before, and this makes this project genuine and original with a great potential.

Research questions and goals

The main research question is whether introducing new tools for optimizing postoperative treatment may improve the clinical outcome for the individual patient and patient groups. Until now, there have not been any clinical decision tools available for the specific postoperative period at the ward, and we do not have sufficient knowledge about patients in this vulnerable phase. Short term goals are to determine whether patients would benefit from a tool as ESS for postoperative treatment. Long term goals are to support healthcare providers with needed systematic real-time information about patients in the postoperative setting. We plan to include a project-arm, in which we will integrate telemetrically retrieved physiological data. A digital wireless platform which integrates ESS, respiration rate, patient temperature, ECG and blood pressure readings before-, during and after the first postoperative night is developed (Patient Status Engine, Isansys Lifecare Ltd., UK). This project is a contribution to validate ESS by means of a variety of monitoring tools as the in dedicated groups of surgical patients by using criteria set out by Terwee et al [12]. We expect to reproduce findings from the pilot project with a score reflecting the postoperative status of the patient, and moreover to observe positive effects on early mobilization including a lower incidence of side-effects of medication. If we will be able to achieve such results, we can identify the patient in need of more thorough care, and provide clinical statistics for improved management of groups of patients.

Study design

We regarded a prospective randomized study with two groups as the best choice for answering the question whether patients might benefit from introducing a new clinical decision tool. One group, named Standard Care Group (SCG) (n=100) will receive standard postoperative care and

management. The other group, named Efficacy Safety Score (ESS) (n=100) will receive care and management according to ESS. In the ESS group, we will assess ESS in parallel with the telemetrically retrieved physiological variables. A randomization of the patients to group SCG and ESS will be done a priori by using a simple block randomization and sequentially numbered opaque sealed envelopes (SNOSE) will be produced. After obtaining patients' consent, the nurses at the ward will pick a sealed opaque envelope with the randomization code enclosed for each patient. This takes place at the ward when the patients are prepared for surgery. The nurses including patients will not have access to the envelopes before time of enrolment. Because of the logistics in this situation, and the fact that it is the ordinary ward staffing which is to perform this, we have concluded that the use of SNOSE is the best allocation concealment we can obtain in this situation. The Regional Medical Ethics Committee recognized two different letters of consent to the SCG and the ESS groups to be the best solution, and to secure correct handling of this, the manual way with sealed envelopes is regarded most robust for this study situation. By this method we plan to reduce selection bias to a minimum. See also enclosed flow-chart.

Hospital setting

We plan to perform the study at the surgical ward 3 at St Olav University Hospital, Orkdal, Norway. The regular nursing staff will be collecting the postoperative data after supervision and education by the PhD-candidate and a dedicated project nurse. The patient population at this ward available for this study will be persons planned for scheduled surgery (bariatric surgery, shoulder joint replacements, knee/hip joint replacement, major abdominal surgery (hemicolectomy e.g.,), robot-assisted radical prostatectomy (RARP)) and acute surgery (orthopaedic ankle and hip surgery, acute abdomen) which is at the hospital staying at least 24 hours after surgery. The number of these patients at Orkdal is 8-12 patients a week. Limitations in the number of monitoring devices (two sets) for the ESS group, will limit the number of patients which can be included each day. Based on this we think that a maximum of 6-8 patients per week is a reasonable goal for inclusion. From this a number of 25-35 effective weeks with inclusion would be reasonable.

Inclusion/Exclusion criteria

Inclusion criteria: all subsequent patients undergoing surgery that expectedly will be treated and observed in hospital for more than 24 hours postoperatively. Exclusion criteria: patients < 18 years of age, refusal of participation, poor communication capabilities and surgery performed that is not compatible with anticipated mobilization during the first 24 postoperative hours.

Primary and secondary endpoints

Primary endpoint of this study will be time to full mobilization of the patient, defined as being able to walk more than one step with/without support. Secondary endpoints will be clinically significant reduction (more than 23% [16]) in measured pain evaluated by a 0-10 scale (Verbal Numeric Rating Scale), significant changes in doses (OMEQ) of postoperative administered opioids, re-admissions to the recovery unit, significant increased patient satisfaction of treatment given and reduction in length of hospital stay.

Methods of analysis

Descriptive statistics will be used to compare baseline characteristics between groups, such as type of surgery, type of anaesthesia, regular pain medication, age, relevant comorbidity (Charlson Comorbidity Index), ASA-classification and body mass index. The effect of ESS on the primary outcome (time to mobilization) will be analysed by Kaplan-Meier estimators, and we will also use Cox-regression analysis to adjust for baseline covariates. For the secondary outcomes, we will use linear and logistic regression to estimate differences in means or odds ratios between study groups, depending on the measurement scale. Non-normally distributed variables will be log transformed, or analysed using non-parametric tests. The precision of all estimated effects will be given by a 95% confidence interval. Due to the anticipated positive influence from the ESS group on

postoperative treatment to the SCG, we will also see if there is a progression in eventually differences in the endpoints between the SCG and ESS group.

Sample size

We performed a power analysis based on the sub-group results of a validation study addressing ESS in total 207 patients [11]. Estimates shows that for obtaining a power of 0,8 with alpha cut-off at 0,05 and beta cut-off at 0,2, a sample size of total 130 patients was required to reach a 25% reduction of time until full mobilization (being able to walk one or more steps with/without support). A total sample size of 130 patients was required to reach a 25% reduction in total hospital stay and a total sample size of 506 and 176 patients was required to reach a 25% reduction in pain at rest and at mobilization, respectively. (Kane SP. SampleSizeCalculator. <http://clincalc.com/Stats/SampleSize.aspx>). Except from pain at rest, which is of limited interest in this study, these sample size calculations suggest that a total sample size of 200 (100 in each group) will be sufficient to detect any meaningful effects of the intervention on both primary and secondary outcomes.

Data collection

Patients will be included after giving their informed signed consent. In both groups, a standardized questionnaire (see attachment) focused on postoperative management and satisfaction will be performed 24 hours postoperatively. In group ESS, we will register ESS for the first 24 hours postoperatively. Registration of ESS is to be done hourly for the first four hours, and then every second hour after the patient has arrived to the ward. For all patients the Modified Aldrete Score and the New Early Warning Score [14-16] will be performed for comparison. If ESS>10 in patients of group ESS, the anaesthesiologist on duty might be called upon (not involved in the study) for assistance. He/she will afterwards be asked to evaluate the necessity of the consultation for later sensitivity/specifity test. All the data will be collected by the nurses with the help of a designed program (Patient Status Engine) on tablet PC from Isansys (Isansys Lifecare Ltd., Oxfordshire, UK) that incorporates ESS into their wireless monitoring platform, Patient Status Engine (PSE) which is a CE-approved device (class IIa) designed for use in hospital settings to collect vital parameters. The data is then transferred to a protected data base locally. Statistical analysis will be performed in SPSS.

Patients not going through the scheduled surgery (removed from surgery plan) will be excluded from the study. For patients with a not planned incident/complication during surgery, we will continue the protocol as long as they are return to the ward at Orkdal during the 24-hour period. If they are transferred to another location, they will be excluded from the study.

We are aware the potential bias in influence to the SCG from simultaneously performing the intervention in ESS group and the focus on postoperative treatment.

Organization and collaboration

The project is supported by a research group of internationally recognized specialists in anaesthesiology with specific interest in postoperative care:

- Prof dr med [name], UiO and Oslo University Hospital.
- Prof dr med [name], UiO and Akershus University Hospital.
- Prof dr med [name], Anaesthesia and Critical Care Research Group Tromsø.
- Dr med [name], Akershus University Hospital.
- Prof dr med [name], St Olavs Hospital/Faculty of Medicine NTNU

Progress schedule and publishing plan

The project is part of a present PhD-program at the University of Oslo, which we now will apply for transfer to NTNU and St Olavs Hospital, with mandatory courses and schedule set up according to a signed contract between the PhD-candidate and the university. A plan for three articles is approved:

1. *Development and validation of the Efficacy Safety Score, a novel tool for postoperative patient management: A prospective observational study (published March 2017 [11])*

2. *Postoperative treatment with Efficacy Safety Score and wireless patient monitoring system at a general ward: a prospective randomized controlled study.*
3. *Introducing novel clinical tools in postoperative treatment at the ward. Effects on working situation for care providers, patient safety and quality of care.* (See attached tentative draft for project plan for this.)

The articles will be submitted for publication in well-recognized international journals.

Ethics

The protocol and the informed consent form of this prospective observational study were approved by the Regional Medical Ethics Committee South East (Approval 2017/1903/REK SørØstA).

Written informed consent will be taken from every patient included in the study. Correct handling of medical records and information is of highest importance, and mandatory training will be given to all staff involved.

Reg.nr ClinicalTrials.gov: NCT03438578.

Tables

[figure not shown]
Table 1 Description of Efficacy Safety Score (ESS)

Mental status	Score
Awake and alert patient	0

Awake patient, but influenced by drugs. Difficulties in communication.	5
Acutely confused, upset/uneasy, hallucinated or euphoric patient	10
Unresponsive patient	15*
Postoperative nausea and vomiting (PONV) status	
No postoperative nausea or vomiting	0
Postoperative nausea only	5
Postoperative nausea and vomiting/retching	10
Pain status at rest	
No postoperative pain	0
Low intensity postoperative pain (VNRS 1-3)	1-3
Moderate intensity postoperative pain (VNRS 4-6)	4-6
Severe intensity postoperative pain (VNRS 7-10)	7-10
Pain status during movement	
No postoperative pain	0
Low intensity postoperative pain (VNRS 1-3)	1-3
Moderate intensity postoperative pain (VNRS 4-6)	4-6
Severe intensity postoperative pain (VNRS 7-10)	7-10
General condition status	
No remarks	0
Minor discomfort (e.g. light-headedness, minor itching, blurred vision, decreased urination etc.)	5
Excessive discomfort (e.g. severe dizziness, itching, restlessness, urine retention, sensation of cold/warmth, cold sweating)	10
Acute circulatory abnormalities (blood pressure \leq 80 or \geq 200mmHg, heart rate \leq 40 or $>$ 110)	15*
Acute respiratory abnormalities (dyspnoea, respiration rate $<$ 9 or $>$ 20/min, long pauses in breathing, shallow breathing)	15*

***Any single score of 15 (on either consciousness, circulation or respiration) should call for IMMEDIATE activation of acute assistance with the patient.**

Flowchart of phases in Efficacy Safety Score study, St Olavs Hospital HF, Orkdal B3:

References

1. Le Manach, Y., et al., *Preoperative Score to Predict Postoperative Mortality (POSPOM): Derivation and Validation*. Anesthesiology, 2016. **124**(3): p. 570-9.
2. Maier, C., et al., *The quality of pain management in German hospitals*. Dtsch Arztebl Int, 2010. **107**(36): p. 607-14.
3. Dolin, S.J. and J.N. Cashman, *Tolerability of acute postoperative pain management: nausea, vomiting, sedation, pruritus, and urinary retention. Evidence from published data*. Br J Anaesth, 2005. **95**(5): p. 584-91.
4. Benjamin (22) died after bone fracture, in VG. 2011: <http://www.vg.no/helse/odelagt-i-helsevesenet/artikkelen.php?artid=10093729> (01.12.2015).
5. Got to strong medications - Davoud (23) died, in Nettavisen. 2011: <http://www.nettavisen.no/nyheter/article3257721.ece> (01.12.2015).

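### Simple block randomisation by envelope on one unblinded ward does not secure minimal selection bias; varied, undisclosed blocks and a fixed order of approach would reduce the risk, though not remove it

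*Combined protocol and SAP*

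**What the plan says.** Under Study design, allocation is prepared in advance "by using a simple block randomization and sequentially numbered opaque sealed envelopes (SNOSE) will be produced". After consent, "the nurses at the ward will pick a sealed opaque envelope with the randomization code enclosed for each patient". The stated protection is that "The nurses including patients will not have access to the envelopes before time of enrolment". The section justifies envelopes partly by "the fact that it is the ordinary ward staffing which is to perform this", notes that the ethics committee considered "two different letters of consent to the SCG and the ESS groups to be the best solution", and concludes: "By this method we plan to reduce selection bias to a minimum".

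Under Hospital setting there is one ward, and "The regular nursing staff will be collecting the postoperative data after supervision and education by the PhD-candidate and a dedicated project nurse". That section puts the available flow at 8-12 patients a week. It notes that only two monitoring sets exist for the ESS group and that "a maximum of 6-8 patients per week is a reasonable goal for inclusion". The Inclusion/Exclusion criteria call for consecutive patients and include one exclusion that needs judgement, on ability to communicate.

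The protocol does not give the block size, whether it varies, whether staff are kept unaware of it, or who generates and holds the list. It also gives no rule for which eligible patients are passed over when there are more than can be included.

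**The concern.** An opaque envelope hides the code inside it. It does not stop anyone working out the next code from those already opened. Blocks force the arms back into balance, so late in a block the remaining allocations can be determined by the earlier ones.

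The setting makes this more relevant than in a blinded or multicentre trial. The arm is evident once assigned, from the consent letter, the hourly or two-hourly scoring and the wireless sensors. The same ward staff enrol, give care and record outcomes. The case mix runs from bariatric surgery to acute hip surgery, so staff could plausibly judge at enrolment who will walk early. With two monitoring sets, they also have a practical reason to wonder which arm comes next.

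If staff approach likely early walkers when ESS is expected, or hold them back when standard care is expected, even without intent, the groups differ in prognosis before treatment starts. Time to full mobilisation, the primary endpoint, would then be biased.

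**Working it through.** **Inputs from the protocol.** 200 patients, 1:1 (Sample size); simple block randomisation, size not stated (Study design); 8-12 available and 6-8 included per week (Hospital setting). The protocol gives no figure for predictability, so there is none to reproduce. Its recruitment estimate does agree with these inputs: 200/8 = 25 and 200/6 = 33 weeks, against 25-35 stated.

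**Assumptions.** Block sizes of 2 to 8. An observer who knows the size or set of sizes and remembers all past allocations. This is the best case for a guesser.

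**Step 1: fixed blocks of 2m.** Share of allocations known with certainty = 1/(m+1). Best-guess accuracy = [m + (4^m / C(2m,m) − 1)/2] / (2m). For m = 2: 1/3 = 33.3% certain, and [2 + (16/6 − 1)/2]/4 = 2.833/4 = 70.8% guessed correctly.

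| Fixed block size | Certain | Best guess correct |
|---|---|---|
| 2 | 50.0% | 75.0% |
| 4 | 33.3% | 70.8% |
| 6 | 25.0% | 68.3% |
| 8 | 20.0% | 66.6% |

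Without blocking, a guess is right 50% of the time.

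**Step 2: randomly varied blocks.** 1,000 simulated lists of 200. The observer updates the probability of the next allocation after each patient, knowing the set of sizes but not where blocks end.

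| Random sizes | Certain | Best guess correct |
|---|---|---|
| 4, 6 | 5.4% | 69.3% |
| 4, 6, 8 | 2.3% | 68.0% |
| 6, 8, 10 | 1.5% | 66.4% |

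**Step 3: room to act.** Pairing the lower and upper ends of the two ranges, 6 of 8 or 8 of 12 patients are included, so 2 to 4 a week are not. Some of these will be refusals or exclusions.

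**Step 4: what acting on it could do (illustration only).** Suppose patients expected to be 10% faster are steered to ESS and patients 10% slower to standard care. The protocol gives no mean or SD. I take the coefficient of variation (CV) implied by its total of 130 for a 25% reduction, with two-sided alpha 0.05 and power 0.80: 0.25 × √(65/2) / (1.960 + 0.842) = 0.51. The standard error of the difference with 200 patients is 0.51 × √(4/200) = 7.2% of the mean.

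- Fixed blocks of 4, acting only when certain: 2 × 10% × 1/3 = 6.7%, which is 0.92 standard errors; type I error about 15%.
- Fixed blocks of 4, acting on every best guess: 2 × 10% × (2 × 0.708 − 1) = 8.3%; type I error about 21%.
- Random 4, 6, 8, acting on every best guess: 2 × 10% × (2 × 0.680 − 1) = 7.2%; type I error about 17%.

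A milder case, a 0.1 SD shift with every guess acted on, gives type I error of about 9% with fixed blocks of 4 and about 8% at a 68% hit rate.

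**The case against.** A reader might infer that the blocks are fixed, that the nurses know their size, and that each enrolling nurse sees every past allocation. The documents say none of this. The word 'simple' suggests a fixed size but does not state one. Keeping the size out of a document that staff can read is sensible in itself. The ward as a whole can observe past allocations, but one nurse working shifts may not follow the sequence.

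A reader might also infer that the trial fails its aim on selection bias. The text states an intention, and predictability is an opportunity for bias, not bias. Several safeguards count: consent comes before opening, nurses have no earlier access to the envelopes, inclusion is meant to be consecutive, and the shortfall in inclusions is attributed to the two monitoring sets, not to nurse discretion. The planned Cox regression adjusts for baseline covariates and would absorb part of any selection on measured prognosis. The type I figures above come from an unadjusted comparison of means, which is not the planned analysis.

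Finally, it is tempting to say that varied blocks cure the problem at no cost. They do not. They nearly eliminate certain allocations but barely change a best guess, and larger blocks permit longer ESS runs.

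All of this stands, and it limits the claim. It does not dispose of it: the physical safeguards do not prevent inference from earlier codes, covariate adjustment cannot reach unmeasured judgement about a patient, and no written rule decides who is passed over.

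**Conclusion.** The concern holds as a modest design weakness. The protocol names a simple block scheme in a setting where past allocations can make some later ones foreseeable, and states no protection against that. If blocks are fixed and staff know or infer the size, 20-50% of allocations (sizes 8 to 2) are certain in advance. With inclusion below the available flow and no rule for who is passed over, minimal selection bias is not secured.

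The documents do not support saying that bias will occur or that the aim has been missed. The range depends on an unstated block size. The bias and type I figures also depend on an assumed prognostic shift, an inferred CV and staff acting on what they foresee. A better scheme is available at very little cost, so this is more than a missing detail, but it is an improvement to make and not a flaw that invalidates the trial.

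**What to change.** Amend Study design to state that:

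- permuted blocks of randomly varying size (for example 4, 6 and 8) are used, generated and held by someone who does not enrol patients, with sizes not disclosed to ward staff;
- each patient is registered before an envelope is opened, and envelopes are opened strictly in number order;
- eligible patients are approached in a pre-set order: operating list for scheduled cases, arrival for acute cases;
- a log is kept of eligible patients not enrolled, with reasons.

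The first item removes nearly all certain allocations. The order of approach and the log limit acting on guesses, which varied blocks alone do not.

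The cost is small. The list has to be generated anyway. Final arm sizes differed by at most 2 patients of 200 in the simulated lists with sizes 4, 6 and 8, an efficiency loss of (2/200)² = 0.01%. Fixed blocks of 4 allow at most 4 ESS allocations in a row (2 + 2 across adjoining blocks), while blocks of up to 8 allow 8 (4 + 4). With two monitoring sets, such a run could delay inclusion, so the largest block should be chosen with that in mind. The log adds a little work for the ward.

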Attachment 1:

MAL FOR INTERVJU 1. POSTOPERATIVE DAG

Efficacy Safety Score

Prosjekt nr: _____

Informert samtykke (sett kryss):

Inngrep: _____

Operasjonsdato: _____

1. **Tidspunkt for mobilisering (gå ett eller flere skritt med/uten støtte):** kl _____

2. **Kan du angi verste smerte siden operasjonen (0-10)?** _____

• Hvilken situasjon utløste verste smerte: _____

3. **Kan du angi gjennomsnittlig smerte siden operasjonen (0-10):** _____

4. **Har du opplevd kvalme etter operasjonen?** Ja/Nei

• Hvis Ja, hvor stor andel av tiden: En episode - litt - halvparten - meste - hele tiden

5. **Har du hatt brekninger og/eller oppkast etter operasjonen?** Ja/Nei

6. **Kan du si noe om nattesøvnen etter operasjonen:**

• Mengde: Ingen – redusert – normal – øket – kraftig øket

• Kvalitet: Normal – urolig/mareritt – urolig/smerte – urolig/vonde tanker

7. **Kan du angi eventuell bekymring/engstelse før operasjonen:**

• Ingen – litt – middels – mye – svært mye

8. **Kan du angi eventuell bekymring/engstelse nå etter operasjonen:**

• Ingen – litt – middels – mye – svært mye

9. **Kan du si noe om din følelse av sikkerhet og trygghet etter operasjonen:**

• Sikker og trygg – stort sett sikker/trygg – verken eller - noe usikker/uttrygg – usikker/uttrygg

10. **Kan du angi din evne til å huske, resonnere, ta beslutninger eller følge med etter operasjonen:**

• Normal - litt redusert – redusert - en del redusert - kraftig redusert

11. **Andre plager eller bivirkninger etter operasjonen?** _____

12. **Kan du angi din grad av tilfredshet med behandling etter operasjonen:**

• Meget utilfreds – litt utilfreds – nøytral – tilfreds – meget tilfreds

13. **Eventuelt andre kommentarer/tilbakemeldinger:**

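### Does the mismatch between the ethics sentence and the consent and randomisation procedure call for a change to the plan?

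*Combined protocol and SAP*

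**What the plan says.** The title describes the project as set on "a general ward: a randomised controlled study", and the Study design section sets out two groups of 100, block randomisation and sealed opaque envelopes.

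On consent, Study design gives an order: "After obtaining patients' consent, the nurses at the ward will pick a sealed opaque envelope with the randomization code enclosed for each patient". It adds that the enrolling nurses cannot reach the envelopes before enrolment. It then reports: "The Regional Medical Ethics Committee recognized two different letters of consent to the SCG and the ESS groups to be the best solution", and gives this as a reason for the envelope method: "to secure correct handling of this, the manual way with sealed envelopes is regarded most robust for this study situation". The Data collection section agrees on the order: "Patients will be included after giving their informed signed consent".

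The Ethics section reads: "The protocol and the informed consent form of this prospective observational study were approved by the Regional Medical Ethics Committee South East".

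Two smaller items bear on the point. The exclusion criteria list "refusal of participation" without a time point. The first-postoperative-day interview sheet in Attachment 1 has a single consent tick: "Informert samtykke (sett kryss".

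**The concern.** Read side by side, the Ethics and Study design sections do not describe the same study. One has an observational design and one consent form. The other has a randomised design and two letters, one per group. From the Ethics sentence alone, a reader could not tell whether the committee approved the randomised protocol.

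The second worry is statistical. A letter written for one group can be matched to a patient only once the group is known, and the protocol links the envelopes to the handling of the two letters. That raises the possibility that a patient signs, or declines, a group letter after the envelope has been opened. Because the refusal exclusion has no time point, it could then remove patients who had already been allocated. At stake would be who counts as randomised, and whether the comparison of time to mobilisation is protected from selection after allocation.

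**Working it through.** **Step 1. Design label.** The Ethics section says observational. The title, the Study design section, the second entry in the article list and Attachment 2 all say randomised. Within the protocol, the observational label otherwise belongs only to the first article, the validation study published in March 2017. The approval reference is numbered 2017/1903, which fits the present trial better than a study already published early that year. That is an inference, but with Study design reporting that the committee considered letters for both groups, it points to a carried-over phrase and not to an approval of something else.

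**Step 2. One form or two letters.** The singular in the Ethics section may be generic. Study design says outright that the committee accepted two letters. The mismatch is weak.

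**Step 3. Order of consent and envelope.** There are three ways to read the procedure:

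| Reading | Consistent with stated order? | Refusal after allocation as part of the consent step? |
|---|---|---|
| A common consent is signed, then the group letter is handed over as information | Yes | No |
| Both letters are presented before opening | Yes | No |
| Only a group letter is signed, after opening | No | Yes |

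Study design and Data collection both put consent first, so only the first two readings fit the text. The visible text does not say which applies. Study design refers to a flow-chart that is not shown, and the consent pages were removed from the copy reviewed.

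**Step 4. Refusal exclusion and tick-box.** Refusal appears in the eligibility list, where it ordinarily means declining to enter. The exclusions that apply after inclusion are given separately at the end of Data collection (surgery cancelled, transfer elsewhere), and refusal is not among them. Attachment 1 is an interview template, not the consent record; the signed letters may carry a date.

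**Step 5. Size, if the third reading were the practice.** The plan gives no refusal rate, so every refusal input here is assumed: no true effect, 100 per arm, a two-sided log-rank test, log-normal times, and all refusals in one arm, drawn from the worst quarter of a pre-operative trait correlated r = 0.3 to 0.5 with log time.

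- Coefficient of variation implied by the planned total of 130 (65 per arm) for a 25% reduction: 0.25 × √(65 / (2 × (1.960 + 0.842)²)) = 0.509.
- Log-scale standard deviation: √ln(1 + 0.509²) = 0.480.
- Mean of the worst quarter of a standard normal trait: 1.271.
- Shift in mean log time with k of 100 removed: k × 1.271 × r × 0.480 / (100 − k).
- k = 5, r = 0.3: 5 × 1.271 × 0.3 × 0.480 / 95 = 0.0096, a ratio of 0.990, or 3.3% of the planned log effect |ln 0.75| = 0.288.
- k = 5, r = 0.5: 0.0161, ratio 0.984, 5.6%.
- k = 10: ratio 0.980 (r = 0.3) or 0.967 (r = 0.5), that is 7.1% or 11.8%.

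Simulated type I error (20,000 replicates per cell, Monte Carlo standard error about 0.0016 near 5%):

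| Refusals, one arm | r = 0.3 | r = 0.5 |
|---|---|---|
| 0 | 5.3% | 5.3% |
| 1 | 5.1% | 5.3% |
| 2 | 5.6% | 5.2% |
| 5 | 5.6% | 5.8% |
| 10 | 6.2% | 8.4% |

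About 10% is reached only near 20 refusals at r = 0.3 (9.9%) or 12 at r = 0.5 (9.7%). That is 20/25 = 80% or 12/25 = 48% of the worst quarter declining one arm only. If fast-recovering patients were the ones to decline, the direction would reverse.

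**The case for a change.** The best case for acting is that the wrong design label stands in the current text. It is not a product of extraction or redaction, and no unseen page can make it right. Explaining it as carry-over accounts for the error without removing it. The gap over group-specific letters is also real: the text ties the letters to the envelopes and does not say what is signed before opening. Clarifying both would take a few words and perhaps two form fields, with no extra patients or procedures.

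Much of this is true. The label is wrong, and the visible text leaves the role of the two letters unexplained. But a low cost does not by itself justify a change. Correcting the label affects no procedure, analysis set or conclusion. Specifying the letters adds detail to an order already given in two places, and the flow-chart or the letters may already contain it. The bias argument needs a departure from the stated order, and the plan offers no evidence of one.

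**Conclusion.** No change to the plan follows. The observational label in the Ethics section is a clerical slip; the single consent form is at most loose wording. The protocol states that consent precedes the envelope, and under that order allocated patients cannot be lost through refusal at the consent step, so there is no effect on bias, power or type I error. What remains is missing detail about which letter is signed when, which staff running the trial can supply and which pages not available here may already give.

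This rests on the stated order being the practice. If it were not, the assumed scenarios suggest little distortion with up to 5 one-sided refusals (5.8% type I error at most). Serious inflation would need large, selective refusal in one arm, which nothing in the protocol suggests.
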